**Grant Title:** The emergence of abstract structure knowledge across learning and sleep

**NCT number:** NCT05746299

**Date:** November 11, 2021

		Aim 1	Aim 2
4.1 Brief Summary			
4.1	Brief Summary	
The objective of this study is to determine whether learning a category with a certain structure in Stage 1 improves learning of a new category with the same structure in Stage 2. The primary endpoint is accuracy on the missing feature task in Stage 2.
	
The objective of this study is to evaluate the contribution of sleep to the consolidation of abstract structural representations. The primary endpoint is accuracy in the missing feature task in Stage 2, administered after the delay period.

4.2 Study Design			
4.2.a	Narrative Study Description	
Participants will be randomly assigned to a Congruent or Incongruent Structure Group. The intervention consists of a missing feature task in Stage 1 in which each participant learns a novel category whose structure is determined by their assigned group. In Stage 2, we will use another missing feature task to expose participants to a new category whose structure is identical to the category learned by the Congruent group in Stage 1. We will assess the effect of our intervention by comparing accuracy on the missing feature task across groups in Stage 2. Our planned sample size of <math>N=100</math> results in statistical analyses with <math>N=50</math> which is sufficient to detect our expected effects.
	
Aim 2 includes Stage 1, a delay, and Stage 2. Participants are assigned to different experimental conditions such that some participants learn only Lattice categories in Stage 1 (Incongruent) while others are exposed to a Modular category (Congruent). Participants are also assigned to Awake or Sleep groups. Categories in Stage 1 are paired with different auditory tones to be used later in TMR in the sleep groups. All participants learn a new Modular category in Stage 2. The Awake participants (Incongruent and Congruent) remain awake during the 2 hour delay between Stage 1 and 2. Sleep participants are given a nap opportunity during the delay while sleep stages are monitored with EEG. For participants who learned a Modular as well as a Lattice category in Phase 1, TMR will be used to selectively activate the Lattice (Incongruent) or Modular (Congruent) category. Participants in the Sleep Control group learned two Lattice categories in Phase 1 one of which will be reactivated with TMR. We will assess the effect of our intervention by comparing missing feature task accuracy in Stage 2 across groups. Accounting for an expected 20% attrition rate in the sleep groups, we plan to collect data from 173 participants, resulting in a final planned sample size of <math>N=150</math>. This results in statistical analyses with <math>N=30</math> which is sufficient to detect our expected effects, based on previous studies using these methods.

4.2.b	Primary Purpose	Basic Science	Basic Science
4.2.c	Interventions		
	Intervention Type	Behavioral	Behavioral
	Name	Learning either a Modular or Lattice category in Phase 1	Awake vs. Sleep, Lattice vs. Modular category in Phase 1, and TMR for either abstract Modular or Lattice structure during the sleep period
	Description	Participants will either learn a Modular or a Lattice category in Phase 1. Then all participants will learn a new Modular category in Phase 2. Ability to learn the new Modular category will be assessed to determine effect of intervention.	The Awake vs. Sleep intervention determines whether participants remain awake or take a nap during the delay period. The Lattice vs. Modular intervention determines whether participants learn two Lattice categories in Phase 1, or one Lattice and one Modular category. The TMR intervention determines whether TMR is used to reactive a Lattice or Modular category during the nap session. After the delay, ability to learn a new Modular category in Phase 2 will be assessed to determine effect of interventions.
4.2.d	Study Phase	Other	Other
4.2.e	Intervention Model	Parallel: Participants will either learn a Modular or a Lattice concept in Phase 1.	Parallel: Participants will be assigned to either an Awake-Congruent, Awake-Incongruent, Sleep-Congruent, Sleep-Incongruent, or Sleep-Control group.
4.2.f	Number of Arms	2	5
4.2.g	Masking	Participant, investigator	Participant
	Allocation	Randomized	Randomized
	Enrollment	100	173
4.3 Outcome Measures			
4.3	Name	Structure knowledge for a new Modular category in Stage 2.	Structure knowledge for a new Modular category in Stage 2.
	Type	Accuracy	Accuracy
	Time Frame	Final accuracy is collected in a missing feature task which occurs 25 minutes after the experiment begins and takes 25 minutes to complete. Stage 1 and Stage 2 will take 50 minutes to complete.	Final accuracy is collected in a missing feature task which occurs 2 hours and 50 minutes after the experiment begins and takes 25 minutes to complete. Stage 1, Stage 2, and the intervening delay period will take 3 hours and 15 minutes to complete.
	Brief Description	The outcome measure is accuracy (0-100%) on the missing feature task in Stage 2.	The outcome measure is accuracy (0-100%) on the missing feature task in Stage 2.
4.4 Statistical Design and Power			
	# of subjects	100	150
	Expected effect size	0.85	0.85
	Power	0.98	0.85
	Statistical methods	T-test comparing accuracy between groups ( $N=50$ each group)	T-test comparing accuracy between groups ( $N=30$ each group)
4.5 Subject Participation Duration			
	Time to complete study	1 hour	3.5 hours
4.6 FDA-regulated intervention?			
	Yes/No	No	No
4.7 Dissemination Plan

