## **Statistical Analysis Plan**

For Aim 1, the outcome measure is accuracy (0-100%) on the missing feature task for the Modular category in Stage 2. The statistical method we will use to assess this outcome measure will be a two-sample t-test to compare accuracy on the new Modular category in Stage 2 across groups (Congruent vs. Incongruent).

For Aim 2, the outcome measure is accuracy (0-100%) on the missing feature task for the Modular category in Stage 2. The statistical method we will use to assess this outcome measure will be a two-sample t-test to compare accuracy across groups (Congruent vs. Incongruent, Awake vs. Sleep).

Our statistical methods are appropriate given comparable research on category learning and structure learning.

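### Aim 2 allows for 20% loss in the nap arms and none in the awake arms, so the unadjusted Awake vs. Sleep t-test is exposed to selection bias if that loss is related to Stage 2 accuracy

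*Protocol*

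**What the plan says.** Protocol 4.2.e sets out five randomised Aim 2 arms: "Participants will be assigned to either an Awake-Congruent, Awake-Incongruent, Sleep-Congruent, Sleep-Incongruent, or Sleep-Control group". Two are awake and three are nap arms. Section 4.2.c treats the delay condition as an assigned intervention: "The Awake vs. Sleep intervention determines whether participants remain awake or take a nap during the delay period".

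On numbers, the Aim 2 narrative in 4.2.a says "Accounting for an expected 20% attrition rate in the sleep groups, we plan to collect data from 173 participants". The same narrative puts the number left for analysis at 150. The enrolment row gives 173 and the power section (4.4) gives 150. The test in 4.4 is a "T-test comparing accuracy between groups ( $N=30$ each group").

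The Statistical Analysis Plan for Aim 2 names a "two-sample t-test to compare accuracy across groups (Congruent vs. Incongruent, Awake vs. Sleep").

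The available text gives no reason for or timing of the nap-arm loss, no definition of the analysis set, no baseline adjustment and no sensitivity analysis.

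**The concern.** Random assignment makes the awake and nap participants comparable at the start. The planned 150 no longer has that guarantee, because the expected loss falls in one delay condition only: about four fifths of the nap participants are compared with all of the awake participants. If those lost would have scored differently in Stage 2 from those retained, part of any Awake vs. Sleep difference reflects who remained and not what sleep did. Losing low scorers would inflate an apparent benefit of sleep; losing high scorers would hide one.

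This matters because the Aim 2 objective (section 4.1) is the contribution of sleep to consolidation, and Awake vs. Sleep is one of the two contrasts the SAP names. It is not the only evidence on that objective, since the cueing (TMR) contrasts among the nap arms also bear on it. Those arms share the same planned loss rate and are less exposed.

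**Working it through.** **Inputs from the protocol.** 20% attrition in the sleep groups, 173 enrolled and 150 final (4.2.a); five arms, two awake and three nap (4.2.e); 30 per group (4.4), hence 2 × 30 = 60 awake and 3 × 30 = 90 nap participants analysed; expected effect size 0.85 (4.4), taken here as a standardised difference.

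**Reproducing 173.**
- Nap arms inflated, awake arms not: 90/(1 − 0.20) = 112.5, rounded up to 113; 113 + 60 = 173. Exact match.
- Rounding up per nap arm: 30/0.80 = 37.5, so 38; 3 × 38 + 60 = 174. One more than stated, same structure.
- All five arms inflated: 150/0.80 = 187.5, so 188. No match.
- A 5% awake loss: 112.5 + 60/0.95 = 175.7, about 176. No match.

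The stated enrolment therefore contains no allowance for awake loss.

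**Implied loss.** 173 − 150 = 23. Nap arms: 23/113 = 20.4%. Awake arms: 0/60.

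**Illustration of bias.** These assumptions are mine, not the documents': no true effect, two-sided alpha 0.05, unit SD, and the nap participants lost are the lowest 20% on a trait with correlation rho to Stage 2 accuracy. The retained nap mean then shifts by rho × φ(−0.8416)/0.80 = 0.35 × rho SD. The rejection rates allow for the smaller variance left after the lowest 20% are removed; they were obtained by simulating the t-test.

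| rho | Shift (SD) | Share of 0.85 | False positives, 30 vs 30 | False positives, 60 vs 90 |
|---|---|---|---|---|
| 0 | 0 | 0% | 0.05 | 0.05 |
| 0.3 | 0.105 | 12% | 0.07 | 0.10 |
| 0.5 | 0.175 | 21% | 0.10 | 0.19 |
| 1 | 0.35 | 41% | 0.32 | 0.67 |

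The last column applies only if the awake arms and the nap arms are each pooled, which the SAP does not state. The 30 vs 30 column follows the group size in 4.4.

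**Price of an as-assigned analysis.** If all of the 20% gain nothing from the nap condition, the effect dilutes to 0.80 × 0.85 = 0.68. Power from the noncentral t (two-sided 0.05) is then about 0.78 for 30 vs 38, against the 0.85 stated in 4.4.

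**The case against.** The strongest reply is that 20% is an enrolment allowance, not an analysis rule. The protocol does not say that people with Stage 2 scores will be excluded, and it does not mention failure to sleep as a reason for loss. If the losses are equipment failures, they are unrelated to accuracy and the contrast is unbiased. If people leave before Stage 2, analysing everyone with a score gives back much the same 150. This is also a basic-science study of consolidation, for which a comparison restricted to people who slept is a defensible target.

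Much of this stands, and it rules out three stronger readings that a reader might infer:
- **That unequal loss biases the contrast whatever its cause.** It does not; at rho = 0 there is no bias.
- **That the investigators plan to discard scored participants who did not nap.** No text says so.
- **That the N=150 analysis is wrong and must become secondary.** Which set is primary depends on whether the target is the effect of sleep or of being offered a nap. The documents do not settle that, and this point does not require it.

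The reply does not remove the asymmetry, which is the plan's own figure. An unstated cause leaves the contrast unprotected; it does not show that the loss is harmless.

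**Conclusion.** The point holds as a conditional risk to Awake vs. Sleep. Expected loss of about 20% in the nap arms and none in the awake arms is built into the 173. That the loss follows randomisation is not written out, but it follows from attrition being stated by assigned group in a randomised design with 173 enrolled. Whether bias results, in which direction and how large, cannot be determined from the documents. Under the assumptions above, the false-positive rate for 30 vs 30 runs from the nominal 0.05 (loss unrelated to accuracy) through about 0.07 to 0.10 (moderate correlation) to 0.32 (the extreme case). It would be higher if the arms were pooled. Inexpensive protection is worth adding; the documents do not support a claim that the planned result is biased.

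**What to change.** In the SAP:

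1. For Awake vs. Sleep, compare arms that learned the same Stage 1 categories and adjust for Stage 1 missing-feature accuracy. It is measured before the delay, so the nap cannot affect it, and adjusting should also help precision. List the pairs explicitly: on my reading of 4.2.a, the Awake-Incongruent arm learned only Lattice categories, as did Sleep-Control, whereas Sleep-Incongruent also learned a Modular one. Pairing by label would therefore mix different Stage 1 content.
2. Run the scheduled Stage 2 task in every nap participant still present. Report an as-assigned analysis of all participants with a Stage 2 score (up to 173) beside the N=150 analysis, and draw a conclusion about sleep only if the two agree or the difference is explained.
3. State the expected reasons for and timing of loss, and fix the rules that produce the N=150 set before Stage 2 accuracy is seen. Report loss by arm with reasons, and the Stage 1 accuracy of those lost and retained.

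The cost is SAP wording, plus the 25-minute Stage 2 task for any nap participant who would otherwise not have been tested. No extra recruitment is needed. The as-assigned estimate may be diluted, as shown in the working, but the N=150 result is still reported.

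One limit remains: step 2 does not recover people who leave before Stage 2. For them the protection is steps 1 and 3, and adjustment removes only the part of the selection that Stage 1 accuracy captures.

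### Aim 2 drops the investigator masking that Aim 1 has, although Stage 1 structure and the TMR-cued category could be coded away from staff; the entry should be stated factor by factor

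*Protocol*

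**What the plan says.** Protocol 4.2.g (Masking) has one entry per aim. Aim 1 reads "Participant, investigator". Aim 2 names only the participant. No reason is given for the difference, and neither entry says which manipulated factor it covers.

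Aim 2 manipulates three things (Protocol 4.2.c):

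- **Awake or Sleep.** "The Awake vs. Sleep intervention determines whether participants remain awake or take a nap during the delay period". The narrative in 4.2.a adds: "The Awake participants (Incongruent and Congruent) remain awake during the 2 hour delay between Stage 1 and 2". For the nap groups: "Sleep participants are given a nap opportunity during the delay while sleep stages are monitored with EEG".
- **Stage 1 structure.** Participants learn either two Lattice categories or one Lattice and one Modular category.
- **TMR cue.** "Categories in Stage 1 are paired with different auditory tones to be used later in TMR in the sleep groups". For those who learned one category of each kind, "TMR will be used to selectively activate the Lattice (Incongruent) or Modular (Congruent) category".

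The endpoint in Protocol 4.3 is task accuracy: "The outcome measure is accuracy (0-100%) on the missing feature task in Stage 2". For Aim 2 the SAP names a "two-sample t-test to compare accuracy across groups (Congruent vs. Incongruent, Awake vs. Sleep"). It does not mention masking.

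**The concern.** Investigator masking is present in the simpler aim and absent in the more complicated one. Aim 1 is two learning tasks in one sitting. Aim 2 puts a two-hour delay between them and, in three of its five groups, a nap with EEG monitoring, cue delivery during sleep and an expected 20% attrition. Each of these is a point at which someone may have to make a decision about a participant after allocation.

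If the person deciding when a cue is delivered, or whether a participant's nap counts, knows which category is being cued, those decisions can differ between groups without any intent. The contrast most exposed is Sleep-Congruent vs. Sleep-Incongruent. Its two groups have the same Stage 1 content and both nap, so apart from the cue there should be nothing to tell them apart. Unmasked decisions would weaken the design's best-controlled test of cueing.

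A second, smaller matter is that a single word for three factors leaves the reader unsure what is protected. Participants know whether they had a nap opportunity, so participant masking cannot extend to Awake vs. Sleep, which the SAP tests.

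**Working it through.** The plan states no figure for masking, so the check is a comparison of the text, with one piece of arithmetic for the number of participants involved.

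**1. What each group experiences in Aim 2** (Protocol 4.2.a, 4.2.c, 4.2.e)

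| Group | Stage 1 categories | Delay | Category cued |
|---|---|---|---|
| Awake-Congruent | includes a Modular | awake | none |
| Awake-Incongruent | Lattice only | awake | none |
| Sleep-Congruent | one Modular, one Lattice | nap | Modular |
| Sleep-Incongruent | one Modular, one Lattice | nap | Lattice |
| Sleep-Control | two Lattice | nap | one of the Lattices |

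**2. What separates the groups, and whether it can be concealed**

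- *Sleep-Congruent vs. Sleep-Incongruent:* only the replayed tone differs. If the tone-to-category map is coded, and the pairing varies between participants so that the sound itself does not identify the category, staff cannot tell the groups apart from the cue.
- *Awake-Congruent vs. Awake-Incongruent:* only Stage 1 structure differs. Aim 1 allocates the same kind of content and lists the investigator as masked to it.
- *Sleep-Control vs. the other nap groups:* Stage 1 structure again, and possibly the cue. The two points above apply.
- *Awake vs. Sleep:* neither participant nor session staff can be masked. One group stays awake and the other is given a nap with EEG.

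Two of the three factors can therefore in principle be masked from both parties, and the third from neither.

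**3. How many participants are involved**

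Inputs: 30 analysed per group (Protocol 4.4), three sleep groups, 20% attrition in the sleep groups, and 173 enrolled for 150 analysed (4.2.a).

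- Nap groups analysed: 3 × 30 = 90. Enrolled: 90 / 0.80 = 112.5, about 113.
- Awake groups: 2 × 30 = 60, with no inflation.
- Total: 113 + 60 = 173, which reproduces the plan's enrolment.
- Expected losses in the nap groups: 113 − 90 = 23.
- For Sleep-Congruent vs. Sleep-Incongruent alone: 2 × 30 / 0.80 = 75 enrolled, 60 analysed, 15 lost.

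The cue contrast thus expects to lose 15 of 75 participants, and the plan gives neither a rule for these losses nor the person who applies it. That describes the opportunity for bias. It does not measure bias: the documents contain nothing from which a shift in accuracy could be derived.

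**The case against.** The strongest reply has four parts.

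*The endpoint is an accuracy score, not a staff rating.* This stands as far as it goes. Nothing suggests that staff score responses, so the most direct route for investigator bias is narrow. Influence on cue delivery and on who stays in the analysis would remain, since both act before or outside scoring. That accuracy also depends on participants' effort is plausible, but the documents do not say it.

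*The routes described are supposition.* This also stands. The documents do not say who starts or stops cueing, whether cueing is automated, who decides that a nap is usable, or who runs Stage 2. A reader might infer from the missing word that session staff know the cue and that the Aim 2 result is biased. The text does not show either. It shows only that the plan does not claim the protection in Aim 2 that it claims in Aim 1.

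*Aim 1 has no cueing, so its masking proves nothing about TMR.* This is correct for cue delivery. Aim 1 supports feasibility for structure only. Feasibility for the cue rests on the two nap groups being identical apart from the tone.

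*The participant entry is not wrong.* Agreed. A reader might infer that it is false because nobody can be masked to napping. The entry does not say which factor it covers, and participant masking can hold for structure and cue. It is incomplete. Declaring Awake vs. Sleep open removes no bias; it only states correctly what protection that contrast has.

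**Conclusion.** The point holds as a design improvement that should be made. As written, the plan leaves the investigator unmasked in the aim where staff handling after allocation is likely to be greater, although two of its three factors appear maskable.

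The size of any bias cannot be computed and none is claimed. What can be counted is the setting in which it could arise: about 113 nap enrolments with about 23 expected losses, or 75 and 15 for the Sleep-Congruent vs. Sleep-Incongruent contrast.

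The conclusion assumes that at least some cue-delivery or exclusion decisions involve human discretion, and that tones can be assigned to categories under a code. If cueing is already automated and exclusions are already decided by someone without access to the allocation, there is no gap in conduct and the plan need only say so.

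**What to change.** Change the Aim 2 entry in Protocol 4.2.g to: *Participant and investigator masked to Stage 1 structure and TMR-cued category; Awake vs. Sleep is open.*

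To make this true in practice:

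- Load the tone-to-category map and the cue under a neutral code, with the pairing varied between participants.
- Keep Stage 1 structure from session staff, as Aim 1 does.
- Hold the code until decisions on nap usability and all exclusions are final, and name the role that makes them.
- Report Awake vs. Sleep as an unmasked comparison.

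The cost is assumed to be small: one table entry, a coded cue file and a key held outside the session team, with no extra staff or participants. The documents do not describe the software, so this should be confirmed. The downside is that Awake vs. Sleep is openly reported as unmasked.

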## **Statistical Analysis Plan**

For Aim 1, the outcome measure is accuracy (0-100%) on the missing feature task for the Modular category in Stage 2. The statistical method we will use to assess this outcome measure will be a two-sample t-test to compare accuracy on the new Modular category in Stage 2 across groups (Congruent vs. Incongruent).

For Aim 2, the outcome measure is accuracy (0-100%) on the missing feature task for the Modular category in Stage 2. The statistical method we will use to assess this outcome measure will be a two-sample t-test to compare accuracy across groups (Congruent vs. Incongruent, Awake vs. Sleep).

Our statistical methods are appropriate given comparable research on category learning and structure learning.

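### Optional precision gain in Aim 2: Stage 1 accuracy could be a covariate wherever the two arms compared had the same Stage 1 content

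*SAP*

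**What the plan says.** The SAP's only method for Aim 2 is "a two-sample t-test to compare accuracy across groups (Congruent vs. Incongruent, Awake vs. Sleep", applied to Stage 2 accuracy. Protocol 4.4 agrees: "T-test comparing accuracy between groups ( $N=30$ each group". Neither names a covariate, a significance level or the pairs of arms to be tested.

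There are five arms (4.2.e): Awake-Congruent, Awake-Incongruent, Sleep-Congruent, Sleep-Incongruent and Sleep-Control. Four statements bear on what each arm learned in Stage 1, which the protocol also calls Phase 1:

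- General sentence (4.2.a): "some participants learn only Lattice categories in Stage 1 (Incongruent) while others are exposed to a Modular category (Congruent".
- TMR sentence (4.2.a), on "participants who learned a Modular as well as a Lattice category in Phase 1, TMR will be used to selectively activate the Lattice (Incongruent") or the Modular category (Congruent).
- Sleep-Control (4.2.a): "Participants in the Sleep Control group learned two Lattice categories in Phase 1 one of which will be reactivated with TMR".
- Interventions (4.2.c): "The Lattice vs. Modular intervention determines whether participants learn two Lattice categories in Phase 1, or one Lattice and one Modular category".

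On timing, 4.2.a says: "The Awake participants (Incongruent and Congruent) remain awake during the 2 hour delay between Stage 1 and 2".

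**The concern.** Stage 1 accuracy comes from the same participants, shortly before the outcome and before nap, wakefulness or TMR can act. To the extent that it predicts Stage 2 accuracy, the unadjusted t-test leaves explainable variation in the error term. Between arms with the same Stage 1 content it is a true baseline, so using it can narrow the interval without new participants.

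The restriction to the same content matters. Where Stage 1 content differs between the arms, Stage 1 accuracy is itself affected by what was assigned, and adjusting for it could remove or distort the effect under study. Which contrasts qualify depends on what Sleep-Incongruent learned, and 4.2.a is not consistent on that.

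**Working it through.** **Inputs.** From protocol 4.4: d = 0.85, n = 30 per arm (150 over five arms), stated power 0.85. Assumed because not stated: two-sided alpha 0.05, with 0.025 as a variant, and a Stage 1 to Stage 2 correlation r from 0 to 0.6.

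**The plan's own figure.** The noncentrality is d·√(n/2) = 0.85·√15 = 3.292 with 58 degrees of freedom. Power is 0.899 at two-sided 0.05, above the stated 0.85. At two-sided 0.025 it is 0.836 (0.853 by normal approximation), which is close to the stated figure, but the documents mention no such level.

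**Timing.** The Aim 2 Stage 2 task starts at 2 h 50 min (4.3). Less the 2 h delay, this leaves 50 minutes for Stage 1, all of it before the delay.

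**Which pairs share Stage 1 content.** Awake-Congruent and Sleep-Congruent learned one Modular and one Lattice category. Awake-Incongruent and Sleep-Control learned Lattice only. Sleep-Incongruent depends on the sentence used.

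| Pair | TMR sentence | General sentence |
|---|---|---|
| Sleep-Congruent vs. Awake-Congruent | same | same |
| Sleep-Congruent vs. Sleep-Incongruent | same | different |
| Sleep-Incongruent vs. Awake-Incongruent | different | same |
| Sleep-Control vs. Awake-Incongruent | same | same |
| Sleep-Incongruent vs. Awake-Congruent | same | different |
| Sleep-Control vs. Sleep-Incongruent | different | same |

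The other four of the ten pairs differ under both sentences. The first three rows each change one of the SAP's two factors. The SAP's comparison list does not name Sleep-Control, and the fifth row changes both factor labels, so the last three rows matter only if the SAP tests them.

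**Effect of adjustment.** For ANCOVA within two arms there are 57 degrees of freedom. The noncentrality is d·√(n/2) / √[(1 − r²)(1 + t²/58)], averaged over chance covariate imbalance t, which follows a t distribution with 58 degrees of freedom. The standard error ratio is √[(1 − r²)(1 + 1/56)], and the equivalent n is 30 divided by that ratio squared.

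| r | Power (unadjusted 0.899) | Standard error | Equivalent n per arm |
|---|---|---|---|
| 0 | 0.894 | +0.9% | 29.5 |
| 0.2 | 0.906 | −1.2% | 30.7 |
| 0.3 | 0.920 | −3.8% | 32.4 |
| 0.4 | 0.938 | −7.5% | 35.1 |
| 0.5 | 0.959 | −12.6% | 39.3 |
| 0.6 | 0.980 | −19.3% | 46.1 |

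The standard error breaks even where (1 − r²)(57/56) = 1, so |r| = √(1/57) = 0.13. The largest loss, at r = 0, is 0.8992 − 0.8939 = 0.0053, about 0.5 of a power point. At two-sided 0.025 it is 0.8362 − 0.8288 = 0.0074, about 0.7. Simulation with 60,000 runs per cell at r = 0, 0.3, 0.5 and 0.6 gave type I error between 4.9% and 5.0% and power of 0.896, 0.920, 0.959 and 0.980.

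**The case against.** The strongest reply is that this is a preference. The planned test is valid under randomisation, its standard error already allows for chance imbalance in Stage 1 performance, and at two-sided 0.05 its power exceeds the stated value. All of that stands, and it is why the point is an option only.

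The gain may also apply to nothing. It needs three things that the documents do not state:

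- **Pairwise tests.** The SAP names factors, not pairs. Thirty per group fits pairwise tests but does not identify them, and pooled tests would stay unadjusted.
- **Recorded Stage 1 accuracy.** The Stage 1 missing feature task is described for Aim 1 only. Fifty minutes of Stage 1 would fit two 25-minute tasks, but that is inference.
- **A useful correlation.** Up to r = 0.3 the gain is about 2 power points at most (0.920 − 0.899). It becomes material from about 0.4 to 0.5.

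There is a presentational cost too. Under the TMR sentence, Congruent vs. Incongruent would be adjusted in the sleep arms but not the awake arms, and Sleep vs. Awake adjusted within Congruent but not within Incongruent. Reporting the t-test for every contrast keeps a like-for-like set.

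A reader might infer that the t-test is biased or underpowered, or that every comparison, including Aim 1, should be adjusted. The documents support neither. The power figures above answer the first. On the second, Stage 1 content is the intervention itself in Aim 1 and in pairs such as Awake-Congruent vs. Awake-Incongruent.

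**Conclusion.** This is a cheap improvement, not a fault in the plan. Under either sentence of 4.2.a, Stage 1 accuracy is a legitimate covariate for Sleep-Congruent vs. Awake-Congruent. The TMR sentence adds Sleep-Congruent vs. Sleep-Incongruent; the general sentence adds Sleep-Incongruent vs. Awake-Incongruent instead. Sleep-Control pairs with matched content count only if the SAP tests them.

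Relative to the t-test, power changes by −0.5 points at r = 0, +2 at r = 0.3 and +6 at r = 0.5, given d = 0.85, 30 per arm and an assumed two-sided alpha of 0.05. The change in standard error does not depend on d or alpha. Nothing in the documents shows which value of r holds.

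The conflict over Sleep-Incongruent needs settling whether or not a covariate is used, because it decides what the contrasts with that arm compare. It does not make the missing covariate more serious.

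**What to change.** 1. Reconcile the general sentence and the TMR sentence in 4.2.a on what Sleep-Incongruent learned in Stage 1.
2. Confirm that Stage 1 accuracy is scored and recorded in Aim 2.
3. If so, list the pairwise contrasts in the SAP. For each one whose two arms have the same Stage 1 content, pre-specify ANCOVA within those two arms, with mean Stage 1 accuracy over the participant's categories as the covariate. Report the t-test for all contrasts beside it, and state beforehand which result leads.
4. Leave Aim 1, pairs with different Stage 1 content and pooled contrasts unadjusted. Add no contrast for the sake of adjusting it.

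The cost is a short SAP paragraph fixed before the data are seen, with no new participants and no new procedure if Stage 1 accuracy is already recorded. The statistical cost is at most about 0.5 of a power point at two-sided 0.05 (0.7 at 0.025). The reporting cost is that adjusted and unadjusted contrasts stand side by side.
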